## 7.6 ENROLLMENT

For screening, only information available in the medical records will be reviewed. Once a potential subject has been identified, all inclusion criteria and none of the exclusion criteria have been met and the informed consent process has been completed or a waiver of consent has been granted by the HREC/EC, the subject will be considered enrolled and assigned a consecutive Subject Identification (ID) number. Enrollment and assigned Subject ID will be documented on the Screening and Enrollment Log. For bilateral subjects, only one Subject ID will be assigned.

Any subject who provides informed consent or has a waiver of informed consent and is subsequently identified not meeting the required entry criteria is considered to be a screen failure. Demographic information must be captured in the appropriate CRF and the reason for screen failure will be documented on the Screening and Enrollment Log.

Study Protocol—Device	
Safety and Performance of MINITAC® Ti 2.0 Suture Anchor in Extremities	Number: MINI.PMCF.2018.11
	Version: 3.0, 20Aug19
	Page: Page 20 of 56

## 7.7 LOST TO FOLLOW-UP

A subject will be considered lost to follow-up if he/she did not return for follow-up per the Investigator's standard of care follow-up schedule. Information will be documented on the Case Report Form (CRF).

## 7.8 WITHDRAWAL

### 7.8.1 Withdrawal from Study

All reasonable efforts should be made to collect 12 months postoperative data on all subjects enrolled into the study. The Investigator may withdraw subjects from the study for many reasons, including but not limited to the following:

- subject lost to follow-up
- if the Investigator or the Sponsor stops the study for any reason and decides to withdraw subject(s) from the study
- any other significant reason identified by the Investigator

For each case, information will be documented on the CRF, detailing circumstances leading to the withdrawal.

Subjects who drop out or are withdrawn will not be re-entered into the study at a later date.

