### 7.4 SCREENING

Subject screening will include a retrospective chart review. To eliminate the potential for selection bias, Investigators will consecutively screen subjects that have undergone extremities repair using the MINITAC◇ Ti 2.0 Suture Anchor by date of surgery, starting from the earliest surgery date, moving forward in time, up until dates of surgery which are at least 12 months prior to the study start date at each site.

Participating study sites are required to document all screened subjects considered for inclusion in this study on the Screening and Enrollment Log. If a subject is excluded from the study, the reasons for exclusion will be documented on the Screening and Enrollment Log.

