### 7.5 INFORMED CONSENT

Study sites will obtain HREC/EC approval before any study specific activities are performed. The Investigator and the Participating Site shall treat all information and data relating to the Study disclosed to Participating Site and/or Investigator in this Study as confidential and shall not disclose such information to any third parties or use such information for any purpose other than the performance of the Study. The collection, processing and disclosure of personal data, such as patient health and medical information is subject to compliance with applicable personal data protection and the processing of personal data (16,17, 24).

Due to the retrospective nature of the study, a HREC/EC waiver of informed consent for study participation should be requested for those subjects who meet eligibility criteria. If allowed, the retrospective data set will be collected for these subjects. No prospective visits will be performed. In Australia, a waiver or alteration of the requirements for obtaining informed consent may be

Study Protocol—Device	
Safety and Performance of MINITAC® Ti 2.0 Suture Anchor in Extremities	Number: MINI.PMCF.2018.11
	Version: 3.0, 20Aug19
	Page: Page 18 of 56

granted by the HREC/EC under any of the following provisions set forth by the National Statement on Ethical Conduct in Human Research published by National Health and Medical Research Council, Australia (14):

- a) involvement in the research carries no more than low risk to participants
- b) the benefits from the research justify any risks of harm associated with not seeking consent
- c) it is impracticable to obtain consent
- d) there is no known or likely reason for thinking that participants would not have consented if they had been asked
- e) there is sufficient protection of their privacy
- f) there is an adequate plan to protect the confidentiality of data
- g) in case the results have significance for the participants' welfare there is, where practicable, a plan for making information arising from the research available to them
- h) the possibility of commercial exploitation of derivatives of the data or tissue will not deprive the participants of any financial benefits to which they would be entitled
- i) the waiver is not prohibited by State, federal, or international law.

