### **9.1.6 Discontinued Subjects**

Discontinued subjects are those who are withdrawn for reasons of safety or who are lost to follow-up. Discontinued subjects should be documented on the Screening and Enrollment Log.

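### The withdrawal rules let an investigator with access to the charted 6-month outcome withdraw an enrolled subject, and nothing requires that subject's existing chart to be abstracted into the success rate

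*Protocol*

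**What the plan says.** **Timing.** Inclusion criterion 3 (Protocol 7.2) requires subjects to be more than 12 months post-operative. Screening (7.4) runs forward through surgery dates "up until dates of surgery which are at least 12 months prior to the study start date at each site". Section 7.5 adds: "No prospective visits will be performed".

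**Withdrawal.** Section 7.8.1 begins with a duty: "All reasonable efforts should be made to collect 12 months postoperative data on all subjects enrolled into the study". It continues: "The Investigator may withdraw subjects from the study for many reasons, including but not limited to the following". The list names loss to follow-up, stopping of the study by the investigator or sponsor, and "any other significant reason identified by the Investigator". Withdrawn subjects may not be re-entered later. Section 9.1.6 describes a further ground that 7.8.1 does not list: "Discontinued subjects are those who are withdrawn for reasons of safety or who are lost to follow-up". Section 7.7 defines loss to follow-up: "A subject will be considered lost to follow-up if he/she did not return for follow-up per the Investigator's standard of care follow-up schedule".

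**Data after withdrawal.** Section 7.8.3 deals only with withdrawal of consent: data collected up to that point may be used and no more may be collected. It is silent on withdrawal by the investigator.

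**Analysis.** The FAS in SAP 3.2.1 is built from all enrolled subjects and is the only analysis set (SAP 5.8). SAP 5.2 computes percentages on the number of subjects providing data at the time point. SAP 5.6 rules out imputation, and SAP 5.3.4 plans no sensitivity analyses.

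**The concern.** In a prospective trial, withdrawal usually precedes the outcome. Here the order is reversed: the outcome period has passed before a Subject ID is assigned, and the person who may withdraw the subject has access to the chart. An open-ended, discretionary ground for withdrawal then allows a decision made in knowledge of the result.

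Protocol 8.3.1 relies on consecutive enrolment to minimise selection bias. That protects the list of subjects who enter. It does not protect the set who contribute an outcome if subjects can be withdrawn afterwards and their charts left unabstracted. At stake is the single-arm success rate, which is the main result of the study and has no comparator.

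**Working it through.** **Plan's own figures.** Protocol 11 and SAP 5.7 state probabilities of 55.4% (N=30) and 98.8% (N=50) of reaching ±10% precision at an assumed 95% success rate. I took the exact binomial probability that the two-sided 95% Clopper-Pearson interval has a half-width of at most 0.10.
- N=30: the half-width is 0.0857 with 1 failure and 0.1063 with 2, so at most 1 failure is allowed. P = 0.5535.
- N=50: the half-width is 0.0989 with 6 failures and 0.1046 with 7, so at most 6 failures are allowed. P = 0.9882.

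Both figures reproduce and are not in dispute.

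**Is the outcome period over at enrolment?** The 6-month window closes at 182 + 30 = day 212. Subjects are past 12 months, so it is always closed. The 12-month window closes at 365 + 30 = day 395, so for a subject just past day 365 it may still be open. The argument is therefore complete for the primary endpoint and only partial for the secondary.

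**How a subject leaves the rate.**
1. The subject is enrolled and belongs to the FAS.
2. The investigator withdraws the subject under 7.8.1 or 9.1.6.
3. No text requires the rest of the chart to be abstracted, because 7.8.3 covers consent only.
4. If no time-point outcome is entered, SAP 5.2 leaves the subject out of n and SAP 5.6 puts nothing in its place.
5. SAP 5.3.4 means that no alternative rate is shown.

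In the Kaplan-Meier analysis of SAP 5.3.3, a subject with no recorded event is censored at the latest CRF assessment, so an unabstracted failure would not count there either.

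**Size.** Let N be the number enrolled, x the successes, and w the failing subjects with no time-point entry. The reported rate is x/(N − w) instead of x/N, an increase of xw/[N(N − w)]. The documents give no failure or withdrawal counts, so those below are assumed.

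| N | Failures | All counted | One lost | Increase (points) |
|---|---|---|---|---|
| 30 | 2 | 28/30 = 93.3% | 28/29 = 96.6% | 28/(30×29) = 3.2 |
| 30 | 3 | 27/30 = 90.0% | 27/29 = 93.1% | 27/(30×29) = 3.1 |
| 50 | 3 | 47/50 = 94.0% | 47/49 = 95.9% | 47/(50×49) = 1.9 |
| 50 | 4 | 46/50 = 92.0% | 46/49 = 93.9% | 46/(50×49) = 1.9 |

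If every failure were lost, the rate would be 100% in each row.

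**The case against.** The strongest reply is that the protocol contains no removal rule. The bar on re-entry in 7.8.1 does not forbid abstracting a chart that already exists. The only ban on further collection follows withdrawal of consent, and the same section asks for reasonable efforts to obtain 12-month data on everyone enrolled. Data entered before withdrawal stay in the analysis. This stands: a reader might infer that abstraction stops at withdrawal, and no passage says so. What remains is that nothing requires abstraction to continue, while the discretion to withdraw is explicit.

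Other tempting inferences also go too far:
- **Safety withdrawals must be device failures.** Section 9.1.6 does not define its safety reasons, and the wording may be carried over from a prospective template.
- **One missed visit makes a subject lost.** The wording "did not return for follow-up per the Investigator's standard of care follow-up schedule" can equally mean that the subject never came back, and withdrawal is in any case optional.
- **Only consent can end participation.** Section 18 also provides for study or site termination.
- **CRF and log conflict.** Sections 7.7, 7.8.1 and 7.8.2 send the information to the CRF, and 9.1.6 adds the log. The two are compatible.
- **Withdrawn subjects leave the FAS.** They do not.

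There is also real transparency. Reasons for discontinuation are tabulated (SAP 5.4.1), AEs leading to discontinuation are summarised and listed (5.3.6.2), and clinical success status is listed by subject (5.3.3). These make withdrawals visible but do not correct the rate.

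Finally, the available-data denominator can bias the rate with or without a formal withdrawal, and a subject with no charted follow-up stays missing whatever 7.8.1 says. That is true, but it does not excuse a rule that lets outcomes which are in the chart go unrecorded.

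**Conclusion.** The point holds as a gap in the rules. Protocol 7.8.1 and 9.1.6 permit outcome-dependent removal, 7.8.3 does not close the gap, and the SAP would carry the loss into the success rate uncorrected. Each failing subject lost this way raises the rate by about 3 points at N=30 and about 2 points at N=50.

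This rests on three assumptions: failure counts of the size illustrated, withdrawal before the time-point outcome is entered, and no later abstraction. It applies fully to the 6-month endpoint and in part to the 12-month endpoint.

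A reader might infer that such removal was intended or took place; the documents show only that it is possible. A reader might also make much of the rate passing 95% in two of the four examples. That figure is a planning assumption, not a decision threshold, the SAP plans no test or interval, and the other two examples do not reach it. The change is worth making because it removes a route to bias at almost no cost.

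**What to change.** These changes concern study participation and data handling only.

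1. **Protocol 7.8.1 and 9.1.6:** limit subject-level withdrawal to withdrawal of consent, with study or site termination left under section 18. Delete loss to follow-up, safety and the open-ended investigator ground as reasons for withdrawal.
2. **Protocol 7.7:** make loss to follow-up a recorded status, with the date of last chart contact.
3. **Abstraction rule:** state that the existing chart of every enrolled subject who has not withdrawn consent is abstracted to day 395, or to the last record available at abstraction if that is earlier.
4. **Counting rule:** state that any charted device failure or re-intervention up to the time point counts as a failure, even if a scheduled visit was missed.

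No change to FAS membership is needed. The cost is protocol wording and slightly more abstraction for patchy charts, with no added subjects or visits. Subjects with no charted follow-up remain a separate missing-data question.

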### 7.8.2 Subject's Withdrawal of Consent to Participate in Study

Study participation is voluntary, and subjects may withdraw at any point during the study without giving their reason for doing so. Where subjects withdraw consent, the Investigator should make a reasonable effort to ascertain the reason(s), while fully respecting the subject's privacy. The reason for withdrawal will be recorded on the CRF.

### 7.8.3 Use of Data Following Withdrawal

In cases where the subject withdraws consent, the data collected up to the point of withdrawal may be used, but no additional data for that subject may be collected.

Study Protocol—Device	
Safety and Performance of MINITAC◇ Ti 2.0 Suture Anchor in Extremities	Number: MINI.PMCF.2018.11
	Version: 3.0, 20Aug19
	Page: Page 21 of 56

## 8. STUDY DESIGN

[figure not shown]
### 8.1 STUDY DESIGN

This is a retrospective, multi-center, case series study to collect clinical data that will evaluate the safety and performance of the MINITAC◇ Ti 2.0 Suture Anchor for indications in extremities. Up to 3 sites will participate in the study across Australia and the EU, collectively enrolling a minimum of 30 and a maximum of 50 subjects into the study. Each enrolling site will enroll a minimum of 10 subjects.

Data from eligible subjects, who have completed the informed consent process as detailed in section 7.5 will be recorded from the subject medical file on designated CRFs. Data will be collected retrospectively for different time points including preoperative, operative, 6 months post-operative and 12 months post-operative.

Figure 8.1-1 details the different steps of study conduct from screening to enrollment and follow-up.

**Figure 8.1-1: Study Flowchart**

Study Protocol—Device	
Safety and Performance of MINITAC◇ Ti 2.0 Suture Anchor in Extremities	Number: MINI.PMCF.2018.11
	Version: 3.0, 20Aug19
	Page: Page 22 of 56

## 8.2 STUDY ENDPOINTS

### 8.2.1 Primary Endpoint

Clinical success rate (%) of the MINITAC◇ Ti 2.0 Suture Anchor in extremities at 6 months post-operative with clinical success defined as extremity repairs without signs of device failure and/or re-intervention as assessed by the surgeon.

### 8.2.2 Secondary Endpoints

Clinical success rate (%) of the MINITAC◇ Ti 2.0 Suture Anchor in extremities at 12 months post-operative with clinical success defined as extremity repairs without signs of device failure and/or re-intervention as assessed by the surgeon.

### 8.2.3 Other Endpoints

Additional endpoints include surgeon reported outcomes as well as safety endpoints.

Surgeon reported outcomes include specific data collected as standard of care and documented in the medical records. This might include but is not limited to the following:

- Range of Motion (ROM)
- Pain assessed by Visual Analogue Scale (VAS)

Surgeon reported outcomes are optional and will be definitively specified in collaboration with the Investigators once sites have been identified for the conduct of the study.

In addition, a listing of device failure criteria will be collected for subjects that were assessed by the surgeon to have signs of device failure and/or re-intervention and therefore not meeting the definition of clinical success.

Safety endpoints include the collection of the following events from the subjects' medical record:

Study Protocol—Device	
Safety and Performance of MINITAC® Ti 2.0 Suture Anchor in Extremities	Number: MINI.PMCF.2018.11
	Version: 3.0, 20Aug19
	Page: Page 23 of 56

- All adverse events (AEs) and complications occurring from the time of subject enrollment until study termination or study completion including intra-operative adverse events and complications.
- Device related re-intervention.
- Device Deficiencies.

### **8.3 METHODS USED TO MINIMIZE BIAS AND MAXIMIZE VALIDITY**

#### **8.3.1 Retrospective Consecutive Enrollment**

To minimize any potential for selection bias consecutive enrollment will be utilized to retrospectively enroll any subjects encountered that meet the inclusion/exclusion criteria. Consecutive enrollment will be performed starting at earliest surgeries moving forward in time.

#### **8.3.2 Balanced Covariates**

The inclusion/exclusion criteria will be generalizable and applicable to the widest possible subset of the population suffering from problems in the extremities. These criteria will be uniformly applied so as to enroll a cohort of subjects with similar symptoms and clinical requirements. This should maximize the applicability to as many subjects with similar baseline characteristics and help to bolster external validity.

#### **8.3.3 Subject Attrition**

Subject attrition due to reduction in sample size required for precision analysis has been accounted in the sample size calculation so that the estimate of the Confidence Interval (CI) to be obtained will still be valid through the most efficient use of available subjects.

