## 10.1 GENERAL

Smith & Nephew's Global Biostatistics group or designee will conduct the statistical analysis for this study. Unless otherwise stated, all significance tests will be two-sided, performed at the 5% significance level. Resulting p-values will be quoted. Point estimates and their corresponding 95% two-sided confidence intervals will be generated where appropriate. Where data summaries are specified, categorical and ordinal variables will be summarized with frequencies and percentages. Continuous variables will be summarized with the following summary statistics: number of observations, mean, median, standard deviation, minimum and maximum values. All analyses will be performed in SAS 9.3 (or later).

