## 10.4 EFFICACY ANALYSIS

### 10.4.1 Analysis of Primary Endpoint

Clinical success rate at 6 months will be summarized using frequency (N) and percentage (%). A 95% exact CI for a single proportion will be presented for clinical success at 6 months using the Clopper-Pearson method (1934) (4). This analysis will be carried out using the PP population as the primary analysis population with the SAF population used for sensitivity analysis.

Study Protocol—Device	
Safety and Performance of MINITAC® Ti 2.0 Suture Anchor in Extremities	Number: MINI.PMCF.2018.11
	Version: 3.0, 20Aug19
	Page: Page 29 of 56

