## 11. SAMPLE SIZE JUSTIFICATION

This study is precision-based, as a result, the sample size is not based on statistical power calculations.

It is reasonable to assume a success rate of 95% for the MINITAC◇ Ti 2.0 Suture Anchor in this study. With a further assumption of a  $\pm 10\%$  precision in order to obtain a 95% CI of 85% to 100%, enrolling 30 subjects into the study will provide 55.4% probability. Across all investigational sites therefore, a minimum of 30 subjects (minimum of 10 subjects per site) up to a maximum of 50 subjects overall (98.8% probability) across all sites will be enrolled into this study.

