5.2 General Presentation Considerations

As this study is of a descriptive nature, the analysis results will be reported using descriptive statistics.

Continuous data will be summarized in terms of the mean, standard deviation (SD), median, minimum, maximum and number of observations, unless otherwise stated. Continuous data that are expected to be skewed will be presented in terms of the maximum, upper quartile, median, lower quartile, minimum and number of observations. The minimum and maximum will be reported to the same number of decimal places as the raw data recorded in the database. The mean, median, lower quartile and upper quartile will be reported to one more decimal place than the raw data recorded in the database. The SD will be reported to two more decimal places than the raw data recorded in the database. In general, the maximum number of decimal places reported shall be four for any summary statistic.

Categorical data will be summarized in terms of the number of subjects providing data at the relevant time point (n), frequency counts and percentages. Percentages will be presented to one decimal place. Percentages will not be presented for zero counts. Percentages will be calculated using n as the denominator.

Given the small, convenience study sample, as well as the absence of *a priori* statistical hypotheses, no formal tests of statistical significance are planned, and as such, no p-values or statistical intervals will be calculated.

All report outputs will be produced using SAS[®] version 9.3 or a later version in a secure and validated environment. All report outputs will be provided to the Sponsor as individual .rtf files and as a consolidated .pdf document.

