5.7 Determination of Sample Size

This study is precision-based, as a result, the sample size is not based on statistical power calculations. It is reasonable to assume a success rate of 95% for the MINITAC[◇] Ti 2.0 Suture Anchor in this study. With a further assumption of a $\pm 10\%$ precision in order to obtain a 95% CI of 85% to 100%, enrolling 30 subjects into the study will provide 55.4% probability. Across all investigational sites therefore, a minimum of 30 subjects (minimum of 10 subjects per site) up to a maximum of 50 subjects overall (98.8% probability) across all sites will be enrolled into this study.

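### Protocol 8.3.3 says attrition is accounted for in the sample size calculation, but the stated 55.4% and 98.8% assume that all 30 or all 50 enrolled subjects are evaluable

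*Protocol*

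**What the plan says.** Protocol 8.3 lists methods for limiting bias and maximising validity. One of them, 8.3.3, states that subject attrition "has been accounted in the sample size calculation so that the estimate of the Confidence Interval (CI) to be obtained will still be valid".

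The only calculation is in Protocol 11. Its inputs are:

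- the success rate: "It is reasonable to assume a success rate of 95% for the MINITAC" device;
- a margin of plus or minus 10%, described as "precision in order to obtain a 95% CI of 85% to 100"%;
- the number enrolled. At the minimum, "enrolling 30 subjects into the study will provide 55.4% probability". For the maximum, SAP 5.7 repeats the Protocol: "up to a maximum of 50 subjects overall (98.8% probability) across all sites will be enrolled into this study".

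The Synopsis gives the same two probabilities as a range for 30 to 50 subjects.

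The interval method comes from Protocol 10.4.1: "A 95% exact CI for a single proportion will be presented for clinical success at 6 months using the Clopper-Pearson method". Protocol 10.1 makes it two-sided: "Point estimates and their corresponding 95% two-sided confidence intervals will be generated where appropriate".

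On incomplete data, Protocol 7.7 and 7.8 provide for subjects lost to follow-up or withdrawn, and 7.8.1 bars their re-entry. The schedule of events limits collection to what the chart holds. SAP 5.6 imputes nothing. For categorical data, SAP 5.2 defines n as the subjects with data at the time point and adds: "Percentages will be calculated using n as the denominator".

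**The concern.** A calculation that allows for attrition normally shows it in one of three ways: an assumed loss rate, an evaluable number below the enrolled number, or an enrolled number raised to protect a target. Protocol 11, SAP 5.7 and the Synopsis show none of these. They attach each probability directly to an enrolled number.

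If the enrolled number was entered as though every subject would be evaluable, 8.3.3 describes a safeguard that the design does not have. A reader of this post-market follow-up study could then take 55.4% and 98.8% as already discounted for missing 6-month assessments. What is at stake is the accuracy of a stated precision figure. No decision rule or hypothesis test depends on it.

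**Working it through.** **Inputs.** True success rate 0.95 and precision of 10 points (Protocol 11). Two-sided 95% Clopper-Pearson interval (Protocol 10.1 and 10.4.1). n = 30 and n = 50 (Protocol 11, SAP 5.7). Attrition: no figure in either document.

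**Formula.** For a given n, find every count x whose Clopper-Pearson interval (L, U) satisfies (U − L)/2 ≤ 0.10. Then sum the Binomial(n, 0.95) probabilities of those counts.

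**Step 1: reproduce the plan's figures with no attrition.**

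- n = 30. For x = 29 the interval is 82.78% to 99.92%, half-width 8.57 points, which meets the criterion. For x = 28 it is 77.93% to 99.18%, half-width 10.63, which does not. The probability is P(X ≥ 29) = 0.95^30 + 30 × 0.05 × 0.95^29 = 0.2146 + 0.3389 = 0.5535. Stated: 55.4%.
- n = 50. For x = 44 the half-width is 9.89 points, which meets the criterion. For x = 43 it is 10.46, which does not. The probability is P(X ≥ 44) = 0.9882. Stated: 98.8%.

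Both figures reproduce. On the same half-width criterion, Wald, Wilson and Jeffreys intervals give 81.2% and 99.7%, and Agresti-Coull gives 55.4% and 99.7%. Of the methods tried, only Clopper-Pearson returns both stated values.

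**Step 2: is any attrition hidden in n?** Running the formula for every n from 20 to 79, only n = 30 rounds to 55.4% and only n = 50 rounds to 98.8%. The neighbours of 50 are 96.5% (n = 49) and 98.7% (n = 51). The evaluable number in the calculation is therefore the enrolled number.

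**Step 3: vary the evaluable number.** The loss levels are assumptions.

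| Enrolled | Evaluable | Loss | Smallest qualifying x | Probability |
|---|---|---|---|---|
| 50 | 50 | 0% | 44 | 98.8% |
| 50 | 49 | 2% | 44 | 96.5% |
| 50 | 45 | 10% | 41 | 92.7% |
| 50 | 40 | 20% | 37 | 86.2% |
| 50 | 35 | 30% | 33 | 74.6% |
| 30 | 30 | 0% | 29 | 55.4% |
| 30 | 29 | 3% | 28 | 57.1% |
| 30 | 28 | 7% | 27 | 58.8% |
| 30 | 27 | 10% | 26 | 60.6% |
| 30 | 26 | 13% | 25 | 62.4% |
| 30 | 25 | 17% | 25 | 27.7% |
| 30 | 24 | 20% | 24 | 29.2% |

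The break below 26 is an effect of discreteness. From 30 down to 26, one failure still meets the criterion, and fewer subjects make two or more failures less likely. At n = 25, one failure gives an interval of 79.65% to 99.90%, half-width (99.90 − 79.65)/2 = 10.13 points, so only 25 successes out of 25 qualify: 0.95^25 = 0.2774.

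**Step 4: average over random loss.** If each enrolled subject is independently unevaluable with the stated probability:

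| Loss probability | 30 enrolled | 50 enrolled |
|---|---|---|
| 5% | 57.4% | 96.7% |
| 10% | 54.2% | 94.5% |
| 20% | 38.5% | 86.2% |
| 30% | 33.6% | 73.0% |

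**Step 5: what the criterion is.** The reproduced figures are for half-width ≤ 10 points. The probability that the Clopper-Pearson lower limit is at least 85% is 21.5% at n = 30 and 54.1% at n = 50. A restated table should therefore name the half-width criterion, since the Protocol's wording suggests an interval lying within 85% to 100%.

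**The case against.** **Any withdrawn or lost subject invalidates the figures.** A reader might infer this, and the documents do not support it. Only a subject without a usable 6-month assessment reduces n. The window runs from 150 days before to 30 days after day 182, so an assessment from about day 32 (182 − 150) can count. All subjects are already more than 12 months post-operative, and Protocol 7.8.3 allows data collected before withdrawal of consent to be used. A subject lost after an in-window assessment still contributes. SAP 3.5.3 expects much missing data for surgeon-reported outcomes and says nothing similar about clinical success. A loss of 20% or 30% on the primary endpoint is thus a what-if and not a forecast.

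**Attrition always worsens the figure.** This is also tempting, and it is wrong at the minimum size. Losing one to four of 30 subjects raises the probability slightly, so 55.4% is conservative there. That is an accident of the binomial, though, and not an attrition allowance. From 50, every smaller n examined (20 to 49) gives less than 98.8%.

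**The interval becomes invalid.** It does not. Clopper-Pearson keeps its coverage at any n, for the population that the evaluable subjects represent. Read narrowly, the closing words of 8.3.3 about validity are defensible. The statement that attrition was built into the sample size calculation is not.

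**The 30-to-50 range is itself the buffer.** The Synopsis range could be read as indexed by the number contributing, and 92.7%, 86.2% and 74.6% all lie inside it. But no section calls the range an allowance, and Protocol 11 ties each end to enrolment. There is no reserve at either 30 or 50.

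**The consequence is small.** This largely stands. The Synopsis bases the sample on feasibility, and SAP 5.2 and 5.8 drop confidence intervals altogether. SAP 5.7 nonetheless keeps the precision argument and both probabilities, and SAP 5.8 does not correct 8.3.3.

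**Conclusion.** The concern holds in a limited form. Protocol 8.3.3 claims an attrition allowance that Protocol 11, SAP 5.7 and the Synopsis do not contain. The two stated probabilities are arithmetically right for 30 and 50 evaluable subjects, and they apply to 30 and 50 enrolled subjects only if none lacks a usable 6-month assessment.

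The size depends on a loss rate that the documents do not give. Over an assumed loss of 10% to 30% from 50 enrolled, the probability of the stated precision drops by 6 to 24 points (98.8 − 92.7 = 6.1; 98.8 − 74.6 = 24.2). From 30 enrolled, up to four losses leave it slightly higher and the fifth halves it (27.7/55.4 = 0.50). These results rest on the plan's own 95% success rate and on the half-width criterion, which is inferred from the exact match to both stated figures.

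This is an unsupported statement about the design. It is not an arithmetic error and gives no reason to distrust the interval itself.

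**What to change.** Do one of the following.

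- Delete the statement in Protocol 8.3.3 that attrition is accounted for in the sample size calculation.
- Or make it true. In the Synopsis, Protocol 11 and SAP 5.7, give the probabilities by number of evaluable subjects (for example 24, 25, 26, 27, 30, 35, 40, 45 and 50). Name the assumed attrition and say that 30 to 50 are enrolled subjects.

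If the probabilities are kept in any form, state that the criterion is a Clopper-Pearson half-width of at most 10 points, and not an interval lying within 85% to 100%.

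No new disposition output is needed. SAP 5.4.1 already tabulates enrolled subjects and completed 6- and 12-month visits, and SAP 5.2 already reports the number with data at each time point.

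The cost is a few sentences and at most one small table. The quoted probability becomes less favourable for losses from 50 and for five or more losses from 30. No additional subjects and no change in conduct are required.
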